PROTOCOL TITLE: Do Anti-Snoring Appliances Reduce the Amount of Airway Manipulation in Patients Undergoing Anesthetic Sedation? A Prospective Randomized Controlled Trial

PRINCIPAL INVESTIGATOR:

[name].
Department of Anesthesiology
[contact]
[contact]

VERSION DATE: 1.0 January 30, 2023

STUDY SUMMARY:

Investigational Agent(s) (Drugs or Devices)	Anti-snoring Appliances including: Zyppah
IND / IDE / HDE #	Zyppah FDA #K182312
Indicate Special Population(s)	 Children  Children who are wards of the state  Adults Unable to Consent  Cognitively Impaired Adults  Neonates of Uncertain Viability  Pregnant Women  Prisoners (or other detained/paroled individuals)  Students/Employees
Sample Size	28
Funding Source	TBD
Indicate the type of consent to be obtained	 Written  Verbal/Waiver of Documentation of Informed Consent  Waiver of HIPAA Authorization  Waiver/Alteration of Consent Process
Site	 Lead Site (For A Multiple Site Research Study)  Data Coordinating Center (DCC)
Research Related Radiation Exposure	 Yes  No
DSMB / DMC / IDMC	 Yes  No

OBJECTIVES:

Would patients using an anti-snoring appliance intraoperatively require less airway manipulation, interventions, and rescue maneuvers during anesthetic sedation cases compared to those who do not?

Null Hypothesis:

There is no difference in the number of airway manipulations, interventions, and rescue maneuvers during anesthetic sedation procedures when an anti-snoring appliance is used.

BACKGROUND:

Surgical cases requiring sedation by an anesthesia provider, also known as monitored anesthesia care (MAC), are a popular choice for outpatient surgical procedures with benefits of “less physiologic disturbance and a more rapid recovery than general anesthesia” (Das 2015). However, MAC cases still come with risk: per the American Society of Anesthesiologists closed claim database, “the most common malpractice claim is inadequate oxygenation/ventilation, with more than 80% of claims of this nature resulting in brain damage or death” (McMurray 2020). Since 1908, anesthesia providers have been utilizing interventional airway devices that manipulate the soft tissues of the nasopharynx, oropharynx, and hypopharynx to relieve obstruction to support patient ventilation and oxygenation; however, there are few studies that directly compare the efficacy & side effect profiles between these devices (Matioc 2019). Additionally, a recent survey indicates that many anesthesia providers desire an alternative airway intervention device than the current ones most commonly used in current practice (McMurray 2020). We will examine the possibility of using at-home, over-the-counter anti-snoring devices as an intraoperative airway device.

STUDY ENDPOINTS:

PRIMARY ENDPOINT: Combined total number of airway interventions during an anesthetic sedation case – including head tilt/rotation, mandible thrust, chin lift, shoulder lift, neck extension or flexion, tongue pull.

SECONDARY ENDPOINTS:

- Satisfaction of Anesthetist via survey
- Maximum/minimum end-tidal CO₂
- # of times SpO₂ value < 92%
- % of time during the case SpO₂ < 92%
- maximum/minimum SpO₂ value
- EKG analysis that were not recorded as “Normal Sinus rhythm”:
- Heart rate maximum & minimum
- maximum/minimum Systolic, diastolic, and mean blood pressure
- Total dose and type of hypnotic & narcotic given
- Case type
- Case duration
- Baseline characteristics (Age, Gender, BMI)

- Time spent in Phase 2 PACU Recovery
- Adverse events (i.e. regurgitation and aspiration, bronchospasm, cough, case converted to GA)

STUDY INTERVENTION(S) / INVESTIGATIONAL AGENT(S):

We will use anti-snoring appliance devices (specifically the FDA approved Zyppah) to attempt to relieve tissue obstructions that cause snoring during sleep. The application of the devices to the body is less invasive than other common intraoperative rescue airway devices (e.g. nasal trumpets and oral airways) which are not designed to be patient specific.

We will be purchasing the device from the manufacturer's website. We will be purchasing the devices via funds awarded by the James E. Eckenhoff Residents' Research Award.

The device will be stored in the PI's key-locked office, until it is given to a research team member to be given to a subject after recruitment and prior to their procedure. Research personnel will bring the appliance to the preoperative holding area & will help mold it for the patient, and will insert it prior to transport to the operating suite. The device will remain in place until the completion of procedure, unless the anesthesia provider in the room feels it needs to be removed for any reason. The patient or anesthesia personnel can remove the device at their leisure after completion of the procedure.

PROCEDURES INVOLVED:

The study participants will be recruited into two groups: patients wearing an anti-snoring appliance device during an anesthetic sedation procedure; and those who do not wear an anti-snoring device. To ensure anesthetic providers have easy access to the patient's airway for standard of care manipulation (if needed), the patients eligible for this study would be those who are undergoing procedures below the umbilicus (e.g. gynecological, urological, orthopedic, etc.) in addition to having a STOP-BANG score of 2 or greater. This will ensure patient safety and provide a wide demographic of potential subjects to increase the generalizability of the study.

For both patient groups, the study procedure is the same. Eligible patients will be identified by chart review of various elements of the electronic medical record, as follows:

Patients will be identified and be seen by the study team in the pre-operative clinic on 17th floor Lavin and in the holding area to interview individuals who are to undergo eligible anesthetic sedation procedures as above. If the patient agrees to participate in the study, they will be randomized at that time to one of the two groups (anti-snoring appliance device to be used for procedure or not).

The groups in the prospective, randomized, controlled trial in patients undergoing anesthetic sedation procedures will be as follows:

Group #1: Anti-snoring appliance (Zyppah) that will be utilized during their procedure
Group #2: Control group, that will not utilize anti-snoring appliance

Participants will be randomized to treatment groups based on a random computer-generated (<https://www.randomizer.org>). Anesthesia providers will not be blinded to randomization, and research personnel will observe the procedure to collect all outcome measures in this study.

For group 1, the study team will aid them in molding and preparing the device in the pre-operative area. Anesthesia providers will be instructed on how the device works and when to place it (with aid from the research team) in addition to receiving a question and answer sheet and protocol they can follow to take with them to the operating room. Prior to the administration of anesthetic medications, the patient will be aided in inserting the device, and wear it throughout the entirety of the case. Regardless of the group, from the start of sedation until the patient leaves the procedure suite. When an anesthesia provider believes they make a clinically significant airway intervention (either via jaw lift, head turning, etc.) they will be instructed to use the “mark now” icon in the anesthetic record and utilize the free text to indicate what intervention was done and why.

All standard practices and standard monitors for anesthetic sedation cases will be utilized.

A post-survey will be administered to anesthesia providers in group 1 to gauge satisfaction.

Anesthetic record will be reviewed by research team members following the end of the case.

DATA AND SPECIMEN BANKING

We will collect data including reason for procedure, type of procedure, and patient demographics (including medical history, sex, age, and weight); in addition to data collected via electronic chart review including: Documented Obstructive Sleep Apnea (OSA), date of procedure, surgical case length, anesthesia type requested, anesthesia type documented, Provider team staff composition, documented neuraxial or nerve block procedure (if applicable), “in room” time, max/min heart rate, min/max oxygen saturation, number of instance oxygen saturation fell below 92%, % of time during case where oxygen saturation was below 92%, min/max end tidal CO₂, min/max blood pressure, total dose of hypnotic & narcotic given, “out of room” time, adverse events noted in charting, free-text written by providers, and total hospital length of stay.

SHARING RESULTS WITH PARTICIPANTS

Results will not be shared with participants.

STUDY TIMELINES

Individual subjects and anesthetic providers will participate in the study for the duration of their procedure requiring anesthetic sedation. It will take approximately 3 months to enroll participants and approximately 3 months to perform data analysis.

INCLUSION AND EXCLUSION CRITERIA

Inclusion criteria

Adult patients (age 18-89 years old)

Undergoing procedures below the umbilicus requiring anesthetic sedation without an invasive airway

STOP-BANG score of 2 or greater.

English or Spanish language speaking

Exclusion criteria

Patients requiring general anesthesia.

Sleep apnea

Serious breathing or respiratory disorders such as COPD, asthma, emphysema

Poor dental health including severe gum disease, loose teeth, abscess, mouth sores, bleeding gums

Dental implant place within last 3 months

TMJ disorder

Mouth or jaw pain

Full dentures

Wear braces

Sleep with CPAP or other devices

Other special populations (individuals who are not yet adults, prisoners, vulnerable populations, pregnant) will also be excluded.

VULNERABLE POPULATIONS:

Will not be a part of study.

PARTICIPANT POPULATION(S)

Accrual Number:	Category/Group: (Adults/Children Special/Vulnerable Populations)	Consented: Maximum Number to be Consented or Reviewed/Collected/Screened	Enrolled: Number to Complete the Study or Needed to Address the Research Question
Local	Adults	28	28
Study-wide		28	24
Total:		28	24

RECRUITMENT METHODS

Patients undergoing an eligible procedure requiring anesthetic sedation will be identified by the anesthesiology team by chart review and the schedule in the pre-operative clinic on the 17th floor Lavin pavilion prior to their procedure. They may also be approached by the research team the morning of their procedure for possible enrollment into the study. If the potential subject is interested in the study a study team member will ask for the subject's email address to send an Econsent using REDCap for their review.

The source of participants will be NMH pavilions (Galter, Feinberg, Lavin) in addition to Prentice Women's Hospital.

COMPENSATION FOR PARTICIPATION IN RESEARCH ACTIVITIES

There will be no compensation for participation; however, patients who are randomized into one of the anti-snoring device groups will be allowed to keep the device, if they wish.

WITHDRAWAL OF PARTICIPANTS

Patients can withdraw from the study at any time and their data will be deleted, and in no way will this impact their care since the study explicitly does not affect the standard of care. The study team will notify the PI by secure NM or NU email if a subject withdraws from the study.

RISKS TO PARTICIPANTS

No significant risk to the patient exists with the utilization of an anti-snoring device. The devices are non-invasive and can be easily removed by the patient or anesthesia provider, if needed. There is the potential for damage to loose teeth, gums or tongue since this is a moldable mouth guard. There is the potential for loss of confidentiality even with strict measures in place to prevent occurrence.

POTENTIAL BENEFITS TO PARTICIPANTS

If functional, the participants may benefit from utilization of an anti-snoring device by reducing snoring and airway obstruction; which would lead to improved sleep and less fatigue. It may also prevent the use of more invasive rescue airway devices that can cause patient discomfort including damage to the lips, teeth, gums, tongue, naso- and oropharynx.

DATA MANAGEMENT AND CONFIDENTIALITY

Data Statistics:

Preparation: In previous studies looking at patient satisfaction for snoring relief, 570 participants were analyzed with one of the anti-snoring devices resulting in a statistically significant benefit. However, there are currently no large published studies that analyze the use of an anti-snoring devices in the setting of MAC anesthesia. Additionally, there are no large studies comparing the efficacy of traditional invasive airway rescue devices (e.g. oral/nasal airways).

We utilized a study by Qiansong Xiao et al titled “Comparison of Nasopharyngeal Airway Device and Nasal Oxygen Tube in Obese Patients Undergoing Intravenous Anesthesia for Gastroscopy: A Prospective and Randomized Study”, which compared the oxygen saturation levels in patients who did or did not have an invasive nasopharyngeal airway at the beginning of the anesthetic sedation procedure, to perform our power analysis. 260 patients were included and randomized; with 3 patients excluded due to failure of the nasopharyngeal airway. Based on the differences in “change in SpO₂” and “raising the mandible” between their test and control groups, and power analysis was completed with an alpha value of 0.05 and power value of 80%. The n per group that was calculated to provide the appropriate power to identify a statistical difference was 12 patients per study group. To compensate for patients in our study being less obese we increased the number per group to 14 subjects. We plan to approach 28 subjects and randomize 28 patients to 2 groups, allowing for patients who may not end up getting their procedure or instances where data collection is incomplete or absent.

Statistical analysis: Data will be compared between all groups using paired t-test with p< 0.05 required to reject the null hypothesis.

Data Security:

All collected data will be stored in REDcap using NM password protected computers for data entry. Data in REDcap is backed up nightly using NM servers which are only accessible to the NM IT administrator. Paper documents generated during the study will be stored in Arkes Pavilion 10th floor Department of Anesthesiology locked research cabinet. Data both paper and electronic will be destroyed 5 years after the completion of the study using current department policy and approved vendors.

PROVISIONS TO MONITOR THE DATA TO ENSURE THE SAFETY OF PARTICIPANTS N/A

PROVISIONS TO PROTECT THE PRIVACY INTERESTS OF PARTICIPANTS

Patients in this study undergoing a procedure under anesthetic sedation can be stressful. If a subject does not feel comfortable with participating, they will have the option to opt out at any time and it will not impact their care if they choose to do so.

Research staff will interact with anesthesia providers on two occasions (at the beginning for ~10 minutes in the pre-operative area and end of procedure for ~5 minutes in the post-operative care area), staff will interact with participants for ~30 minutes prior to the procedure in the pre-operative area in addition to helping mold the mouthpiece.

COMPENSATION FOR RESEARCH-RELATED INJURY

n/a

ECONOMIC BURDEN TO PARTICIPANTS

There is no cost to the patient to be in this study. The device is being paid for by the Department of Anesthesiology.

CONSENT PROCESS

Introduction of the study to the potential participant and consent will take place in Northwestern Hospital's Lavin Anesthesia Pre-Operative Clinic. The potential participant will then be sent a consent document from REDcap which includes the electronic consent document for their review. If the potential participant consents one of the study team members will contact them to discuss the day of surgery plan. The participant will receive instructions on acquisition and preparation of the device, in addition to instructions on bringing it to the day of their procedure. REDcap electronic consent will be utilized to decrease the number of times the paper consent would be touched. Multiple times throughout the process, the participant will be reminded that this in no way affects their standard of care and that participation can be withdrawn at any time.

NON-ENGLISH SPEAKING PARTICIPANTS

While we do not anticipate non-English speaking participants on this study, if a non-English speaking patient would benefit from enrollment in this study, the investigator will adhere to the IRB's standard requirements for non-English speaking participants.

This includes providing the IRB the following in a timely fashion:

- Certified translations of all documents the participant will be required to complete (such as surveys and questionnaires);
- A qualified translation service will be used to translate patient facing documents and consent forms
- Certified translations of the modified consent document in a language understandable to the non-English speaking participant if the English version of the approved consent document undergoes subsequent modification;

- All patient-facing documents, including consent forms, will be translated into the patient's preferred language. Any modified patient facing document or consent form will be translated by a qualified translation service, submitted to the IRB for approval, and presented to the patient with a translator present to communicate the changes to the patient and to translate any questions the patient might have, in the patient's preferred language.
- Ongoing communication with the participant will be in a language understandable to the participant
- Northwestern Medicine Interpretation services will be contacted by calling [contact]. Face to face interpretation or video remote interpreting (VRI) will be scheduled via NM. This offers remote access to an interpreter via an iPad.
- A qualified translator will be available to translate the consent and any other patient facing document in his or her preferred language. The translator will communicate all questions to the study team member who is obtaining the patient's consent.
- A translator will be available for the entire duration of their participation on the study to translate any questions/requests from the participant to the study team and from the study team to the participant.

Northwestern Medicine Interpretation services will be contacted by calling [contact]. Face to face interpretation or video remote interpreting (VRI) will be scheduled via NM. This offers remote access to an interpreter via an iPad.

WAIVER OR ALTERATION OF CONSENT PROCESS

n/a

PROTECTED HEALTH INFORMATION (PHI AND HIPAA)

- Will a HIPAA Authorization be obtained from for all participants? Yes
- Name
- Age (years)
- Date of procedure
- Telephone numbers
- Medical Record Numbers
- Email address

QUALIFICATIONS TO CONDUCT RESEARCH AND RESOURCES AVAILABLE

The PI has 10 plus years clinical research experience. Northwestern Medical Center cares for thousands of patients who undergo anesthetic sedation procedures each year. The research team includes 2 resident physicians and a research assistant on the anesthesia care team who will assist the PI during the study period.

MULTI-SITE OR COLLABORATIVE RESEARCH:

n/a

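### Should the primary comparison of airway-intervention counts be adjusted for case duration?

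*Combined protocol and SAP*

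**What the plan says.** Under STUDY ENDPOINTS the primary endpoint is the "Combined total number of airway interventions during an anesthetic sedation case", a raw count with no time denominator. The null hypothesis under OBJECTIVES is framed in the same way: "There is no difference in the number of airway manipulations, interventions, and rescue maneuvers during anesthetic sedation procedures" when the appliance is used.

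Under PROCEDURES INVOLVED, the text just before the marking instruction gives a period "from the start of sedation until the patient leaves the procedure suite". The sentence is incomplete, but it reads naturally as the counting window. Eligible surgery spans several specialties and no limit on length is stated. A provider marks an event when he or she "believes they make a clinically significant airway intervention", and "Anesthesia providers will not be blinded to randomization".

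Case duration is listed among the secondary endpoints. DATA AND SPECIMEN BANKING lists surgical case length and the times of entering and leaving the room. The statistical analysis sentence under DATA MANAGEMENT AND CONFIDENTIALITY names a paired t-test at the 0.05 level, with no covariate, offset, rate or stratification.

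**The concern.** A patient sedated for longer has more opportunity to need a jaw or head manoeuvre. If counts rise with time, differing case lengths add noise to a comparison of only 14 patients per arm. A chance imbalance in case length would also pass straight into the estimated device effect. The duration data are being collected anyway, so one covariate in the primary model looks like a cheap gain. What would be at stake is power, and the credibility of a result from a trial in which the arms happened to differ in case length.

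**Working it through.** **The plan's own figure.** The protocol gives 12 per group for 80% power at alpha 0.05, raised to 14, but states no effect size or standard deviation. The 12 therefore cannot be recomputed forward. Solving backwards for an independent-groups, two-sided t-test gives a standardised effect of 1.20. At 14 per arm the same effect has 86.2% power.

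**Break-even for a covariate.** Let r be the within-arm correlation of count and duration. Adjustment multiplies the variance by (1 − r²) × [1 + 1/(2n − 4)], with 2n − 3 degrees of freedom. At n = 14 the second factor is 1 + 1/24 = 1.042. The product equals 1 when r² = 1 − 1/1.042 = 0.04, so r is about 0.2. Power at effect 1.20 is 84.6% at r = 0, 86.1% at 0.2, 87.8% at 0.3 and 93.1% at 0.5. The documents give no value of r.

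**Simulation.** All inputs here are assumptions: 14 per arm, negative-binomial counts, control mean 4, ratio 0.4, dispersion 0.3, log-normal durations, 40,000 trials per scenario. Entries are power (%) for an independent-groups t-test, then for a linear model with group and duration.

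| Scenario | log-SD 0.3 | log-SD 0.5 | log-SD 0.7 |
|---|---|---|---|
| Counts proportional to duration, covariate is the exact window | 70.0 → 72.4 | 58.2 → 68.8 | 44.5 → 63.3 |
| Counts rise with square root of duration | 75.6 → 74.7 | 72.4 → 73.6 | 67.4 → 71.2 |
| Counts unrelated to duration | 77.5 → 75.4 | 77.0 → 74.9 | 77.3 → 75.0 |
| Proportional, covariate is surgical case length, rest of window averages 50% of it | 71.6 → 71.4 | 65.8 → 69.3 | 57.7 → 66.9 |
| Same, rest of window averages 100% | 70.0 → 68.8 | 66.6 → 67.7 | 61.6 → 65.9 |
| Proportional, exact window, device shortens it by 10% | 78.3 → 68.2 | 66.6 → 65.1 | 51.6 → 59.9 |
| Proportional, exact window, device shortens it by 20% | 84.9 → 58.6 | 74.8 → 59.0 | 60.5 → 55.7 |

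The first row is the best case. Surgical case length is only a proxy for the window, so the fourth and fifth rows are closer to what could be achieved with that field. With the 50% proxy the gains fall to about 0/+2/+6 points at control mean 2 and about 0/0/+2 at mean 1. Low counts are plausible because only events judged clinically significant are marked.

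**Validity.** With no device effect, the unadjusted test rejects in 4.2% to 4.9% of trials across control means 1, 2 and 4 and all three relations. Under proportional counts at mean 4, mean durations differ by 30% or more in 2/19/37% of trials. Within those trials the unadjusted test rejects in 13/11/9%, against about 4% adjusted. Over all trials the unadjusted rates are 4.7/4.5/4.2%.

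**What adjustment does to the estimate.** The control mean is 4 and the device mean is 4 × 0.4 = 1.6, a difference of −2.4.

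- If the device shortens the window by 20%, the device mean is 1.6 × 0.8 = 1.28 and the total effect is −2.72. The adjusted estimate is −2.0 to −2.1.
- If it lengthens the window by 20%, the device mean is 1.6 × 1.2 = 1.92 and the total effect is −2.08. The adjusted estimate is −2.5 to −2.6.
- If each intervention adds an assumed 4% of mean case length, the adjusted difference moves from about −2.4 to −2.0. Here duration is partly a consequence of the outcome.

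A comparison of log duration between arms would detect a 20% shortening in only 48/21/13% of trials, so the trial cannot check the assumption that adjustment needs.

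**The case for a change.** The strongest case for a change is this. With 28 patients precision is scarce, and randomisation cannot be trusted to balance case length: the standard error of the difference in mean duration is √(2/14) = 0.38 SD, so a gap above 0.5 SD arises in about 19% of trials. The analysis sentence must be rewritten anyway because a paired test does not suit two separate groups. A covariate would then cost a few sentences and no new data. Fixing its use beforehand would prevent a choice between raw, adjusted and rate analyses after the durations are seen. If counts do not depend on duration, the loss is only about 2 points.

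Much of this stands. The gain is real if counts track the window closely and durations vary widely, and the imbalance figures are correct for the trials they describe. But those trials are picked out by a 30% cut-off, and the overall error rate is sound. The loss of about 2 points assumes that the device leaves duration alone. That may fail just when the device works, because fewer interruptions could mean shorter cases.

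The choice of duration field is not settled either. Room times lie closer to the counting window. They might be affected by device handling, since removal is allowed at any point after the procedure: "The patient or anesthesia personnel can remove the device at their leisure after completion of the procedure". Insertion is less of a worry: "Prior to the administration of anesthetic medications, the patient will be aided in inserting the device", and the section on the study intervention places it before transport to the operating suite. Type of procedure is collected and fixed before randomisation, which avoids the causal problem, but nothing in the documents shows how much precision it would buy in 28 patients.

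**Conclusion.** No change to the plan follows. The raw count matches the stated hypothesis, and an unadjusted comparison of independent groups answers it without bias or inflated type I error. Adjusting the primary test for duration is a trade-off. With surgical case length as covariate the gain is about 0/+4/+9 points at control mean 4 (proportional counts, rest of window 50% of surgical length) and about 0/0/+2 at mean 1. Against that stand losses of about 26/16/5 points, and an estimate reduced from −2.7 to about −2.0, if the device shortened the window by 20%. Every one of these figures rests on assumed counts, dispersion and durations, because the documents give none.

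Analysts may reasonably tabulate case duration by arm, which its listing as a secondary endpoint already invites, and may show a duration-adjusted model as supportive. Neither would alter the primary result. The conclusion presumes that the paired t-test is replaced by a comparison of independent groups, which is a separate point.

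### The EKG and minimum-SpO₂ secondary endpoints have no pre-sedation reference, so a rhythm or saturation the patient arrived with counts as an intraoperative finding

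*Combined protocol and SAP*

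**What the plan says.** - **EKG endpoint (Study Endpoints, secondary list).** The entry reads "EKG analysis that were not recorded as “Normal Sinus rhythm". It gives no onset condition, comparator or start time.
- **SpO₂ endpoints (same list).** These are the "maximum/minimum SpO₂ value" and the number of times and percentage of the case below 92%.
- **Baseline data.** The endpoint list names "Baseline characteristics (Age, Gender, BMI"). Data and Specimen Banking adds "patient demographics (including medical history, sex, age, and weight") and documented sleep apnea.
- **Data to be extracted (Data and Specimen Banking).** The vital-sign items include "max/min heart rate, min/max oxygen saturation, number of instance oxygen saturation fell below 92"%. The list has no rhythm item and no pre-sedation SpO₂.
- **Eligibility (Inclusion and Exclusion Criteria).** Adults aged 18 to 89 are eligible, and no cardiac or rhythm disorder is excluded.
- **Observation window (Procedures Involved).** The nearest statement is a sentence without a main clause: "Regardless of the group, from the start of sedation until the patient leaves the procedure suite".
- **Monitoring (Procedures Involved).** "All standard practices and standard monitors for anesthetic sedation cases will be utilized", and the research team reviews the anesthetic record after the case.
- **Planning (Data Statistics).** The power analysis is "Based on the differences in “change in SpO₂” and “raising the mandible” between their test and control groups" of a cited study.

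**The concern.** An intraoperative outcome should reflect what happens after sedation starts. Read literally, the EKG endpoint also captures what the patient brought into the room. Someone with established atrial fibrillation or a paced rhythm meets it before any drug is given, whichever arm they are in. With so few patients, one or two such people could be most or all of the recorded EKG findings, and a reader would take them for events under sedation.

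Minimum SpO₂ has a milder form of the same problem. A patient who starts low and hardly falls can have the same minimum as one who starts high and falls a long way. The recorded maximum does not settle which, because it can occur at any time, including after oxygen is given. Maximum minus minimum is a range, not a change from a starting value.

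A baseline reading chosen only after the case would also be a matter of discretion, and the anesthesia providers are not blinded.

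**Working it through.** **Plan's own figures.** The plan gives no prevalence of non-sinus rhythm and no SpO₂ distribution, so there is nothing to reproduce on this point. Its 12 per group cannot be rebuilt either, because the means, SDs and rates behind it are not reported. What follows illustrates size under stated assumptions.

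**Inputs.** N = 28, 14 per arm (Data Statistics). Prevalence p of a non-sinus rhythm on arrival is assumed to be 2%, 5% or 10%. No treatment effect on rhythm is assumed.

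**Step 1: patients arriving in a non-sinus rhythm.** Expected number = 28p. P(at least one) = 1 − (1 − p)^28.

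| p | 28p | (1 − p)^28 | P(at least one) |
|---|---|---|---|
| 2% | 0.56 | 0.568 | 43% |
| 5% | 1.4 | 0.238 | 76% |
| 10% | 2.8 | 0.052 | 95% |

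**Step 2: imbalance between arms.** Let b(k) be the Binomial(14, p) probability of k such patients in one arm. Then P(equal) = Σ b(k)², P(differ by exactly one) = 2 Σ b(k)b(k+1), and P(differ by two or more) is the remainder.

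| p | Equal | Differ by one | Differ by two or more |
|---|---|---|---|
| 2% | 0.615 | 0.337 | 0.048 (5%) |
| 5% | 0.383 | 0.445 | 0.172 (17%) |
| 10% | 0.259 | 0.413 | 0.328 (33%) |

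Any inequality at all has probability 38%, 62% or 74%, but most of that at 2% and 5%, and over half at 10%, is a difference of a single patient.

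**Step 3: could this alone produce a significant result?** Two-sided Fisher's exact test with 14 per arm gives:

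- 1 v 0: p = 1.00
- 2 v 0: p = 0.48
- 3 v 0: p = 0.22
- 4 v 0: p = 0.10
- 5 v 0: p = 2 × C(14,5)/C(28,5) = 2 × 2002/98280 = 0.041

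The chance that arrival rhythm alone makes the arms differ by five or more is about 0.5% at p = 10% and below 0.1% at p = 5%.

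**Step 4: minimum SpO₂.** If the correlation between starting and minimum SpO₂ is r, adjusting for the starting value multiplies residual variance by 1 − r². Analysing the simple change multiplies it by 2(1 − r), assuming equal variances. The r values are assumed.

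| r | Adjusted | Simple change |
|---|---|---|
| 0.3 | 0.91 | 1.4 |
| 0.5 | 0.75 | 1.0 |
| 0.7 | 0.51 | 0.6 |

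Adjustment lowers the variance at each of these values. Subtraction raises it at r = 0.3 and leaves it unchanged at r = 0.5.

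**The case against.** **Randomisation handles it.** It balances arrival rhythm and starting saturation in expectation, so neither arm is favoured. This stands, and it limits the harm to misclassification, noise and chance imbalance. It does not make the endpoint measure events under sedation.

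**The data are probably there.** Standard monitors are used, research personnel observe the procedure to collect outcomes, and the record is reviewed. A reader might infer that change in SpO₂ cannot be measured, but the documents do not support that. The reading is not scheduled, defined or listed, yet it may well be in the record. Change in SpO₂ is also not an endpoint of this trial, so no declared endpoint fails for want of it.

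**Baseline data go beyond age, gender and BMI.** Medical history, weight and documented sleep apnea are collected too, so it would be wrong to say that baselines stop at those three. Medical history could reveal a known arrhythmia, but no rule connects it to the EKG endpoint.

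**The list may be looser than a strict reading.** The EKG line ends in a colon and may be a field for naming the rhythm, or sub-items may have been lost in text extraction. The extraction list is introduced as non-exhaustive, so the missing rhythm item is weak evidence by itself. These points are fair, but none supplies a pre-sedation comparator.

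**A window exists.** The fragment in Procedures Involved suggests one starting at sedation. It is incomplete and not tied to the EKG or SpO₂ endpoints, and in-room time is also collected, so earlier readings could enter the extremes.

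**Conclusion.** The point holds as a definitional weakness in secondary endpoints that is cheap to repair. As written, the EKG endpoint counts rhythms that predate sedation, and minimum SpO₂ cannot be separated from starting saturation. Neither causes systematic bias, and the primary endpoint, a count of airway interventions, is unaffected.

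The size rests on an assumed prevalence. From 2% to 10%, at least one misclassified patient among 28 has probability 43% to 95%, and a difference of two or more between arms has probability 5% to 33%. A reader might infer that one or two such patients would decide the comparison. They would not: by Fisher's exact test, 2 v 0 gives p = 0.48 and 5 v 0 is needed for p < 0.05. The damage is to what the reported EKG findings mean. Adjusting minimum SpO₂ is a gain in precision and interpretability rather than the correction of an error, and its size depends on an assumed correlation.

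The mismatch between the variables used for planning and the primary endpoint is a separate sample-size matter. A baseline reading does not resolve it or change the number of patients.

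**What to change.** 1. In Data and Specimen Banking, add for both arms the last rhythm and last SpO₂ recorded before the first sedative dose, noting whether the patient was on room air or oxygen. Add rhythm during the case to the same list.
2. In Study Endpoints, redefine the EKG endpoint as a rhythm that differs from the patient's own pre-sedation rhythm and arises after the start of sedation.
3. Complete the unfinished sentence in Procedures Involved, and state that minimum and maximum SpO₂, the number of episodes and the percentage of time below 92% are taken from the start of sedation.
4. In Statistical analysis, compare minimum SpO₂ between arms with adjustment for the pre-sedation value, for example by analysis of covariance.

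**Cost.** A few more fields from a record already under review, and changes of wording. No new procedure and no change in sample size. Fewer EKG events will be counted, because pre-existing rhythms drop out.
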